11.3.2 Treatment allocation

To preserve masking of subjects and assessors, sham injections will be randomly assigned to either a monthly (SM) or every other month (SEOM) arms, but the two sham groups will be pooled for hypothesis testing (S). Thus randomized treatment allocation will be AM: AEOM: SM: SEOM in a 2:2:1:1 fashion. As above, for analysis SM and SEOM will be pooled into a single group, S.

11.3.3 Treatment efficacy and power analysis

This study is designed to detect a 30% reduction in annual square root area increase. Calculations are provided for three scenarios (Proc Power onewayanova, SAS 9.3)

Square root area change (mm)			Sample size			Power to detect a difference
AM	AEOM	S	AM	AEOM	S	
0.23	0.23	0.33	67	67	67	91%
0.23	0.33	0.33	67	67	67	91%
0.23	0.28	0.33	67	67	67	83%

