5.2 Study Endpoints

5.3 Primary Efficacy Endpoint

To demonstrate superiority of monthly and EOM APL-2 IVT injections compared to sham injections based upon the mean change in GA lesion size as measured by FAF.

- The primary endpoint is the change in square root GA lesion size from baseline to Month 12 as measured by FAF.

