11. STATISTICAL CONSIDERATIONS

Analyses planned during the study include: 1) a primary intention to treat efficacy analysis after all subjects are randomized and complete 12 month follow up; and 2) ancillary analyses which will be conducted on 6 month follow up data and per-protocol analyses at both time points.

All statistical tests will be two-sided with a type 1 (alpha) error rate of 0.1. To understand the clinical significance of the estimated treatment effects and to aid in the interpretation of the formal hypothesis testing, two-sided 95% confidence intervals will be provided.

Descriptive summaries will include mean, standard deviation, median, and range for continuous variables and counts and percentages for categorical variables.

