11.2.3.2 Analytic Methods

Since prior studies have demonstrated that square root area changes are independent of baseline size,^{1,2} we anticipate analysis with one factor Analysis of Variance (ANOVA) and no need for a baseline covariance correction or baseline size stratification. If the overall hypothesis of equality of group means (H_0) is rejected at the 0.1 alpha level, then group means will be compared with post-hoc Least Significant Difference (LSD) multiple comparisons. These multiple comparisons will also be conducted at the 0.1 alpha level.

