11.3.1 Natural history growth rates

Based on two assessments of GA growth measured with Cirrus OCT,^{32,33} we assume that in the absence of treatment average square root area lesion growth is 0.33mm/year (mean of 0.28mm/year³³ and 0.37mm/year³²) and the standard deviation of annual square root area growth is 0.21mm/year.³²

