### **3.3. DETERMINATION OF SAMPLE SIZE**

With a total sample size of 201 evaluable subjects there is approximately 90% power to claim a statistically significant difference in means among treatment groups if there is a 'true' 30% reduction in annual increase of square root GA area for the APL-2 treated groups compared with the pooled sham treatment group. This assumes that, in the absence of treatment, average square root area change is  $0.33\text{mm}/\text{year}^{1,2}$ , the standard deviation of annual square root area change is

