#### **8.1. PRIMARY EFFICACY ENDPOINT AND ANALYSIS**

The primary endpoint is the change from baseline in square root area for GA lesion at Month 12 as measured by FAF. Baseline will be taken as the last available non-missing assessment prior to first study drug administration, this should be the screening assessment for the primary endpoint.

The change from baseline in square root area for GA lesion at Month 2, 6 and 12 will be analysed for the MITT population with a MMRM. The model will include the fixed effects of treatment (3 groups: AM, AEOM and Sham), baseline square root area for GA lesion, visit (2, 6 and 12 months), treatment by visit interaction, visit by baseline interaction and treatment by baseline interaction. An unstructured covariance structure will be used to model the within subject error. The Kenward-Rogers approximation will be used to estimate the denominator degrees of freedom. If the treatment by baseline interaction is not significant at the 10% level then this term will be removed from the model. If significant at the 10% level results will be presented both including and excluding this term and the nature of the interaction will be investigated before deciding on an approach for presenting results that include the treatment by baseline interaction.

All available data will be included in the analysis. The analysis model table will be presented. The treatment comparisons (AM vs Sham, AEOM vs Sham and AM vs AEOM) at Months 2, 6 and 12 will also be presented with the estimate, standard error and 95% CI. If the treatment effect is significant at the 10% level then the treatment means will be compared using the least significant difference (LSD) method and the p-value presented. In addition, the estimated mean (i.e. Least-Squares mean) change from baseline in square root area for GA lesion with  $\pm$  SE of mean change, will be plotted over time by treatment group.

The model assumptions will be checked by evaluating the model residuals. A Shapiro-Wilks test will

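### The stated power (91/91/83%; SAP about 90%) is that of the overall three-group F test; no power is given for showing APL-2 superior to sham, which also needs the LSD step

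*Protocol*

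**What the plan says.** **Aim.** Protocol 5.3, like the Synopsis, sets the primary efficacy aim as "To demonstrate superiority of monthly and EOM APL-2 IVT injections compared to sham injections". Protocol 11.2.3 words it more loosely: whether growth under either the monthly (AM) or the every-other-month (AEOM) regimen differs from sham. The null hypothesis in 11.2.3.1 is equality of all three means.

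**Decision rule.** Protocol 11.2.3.2 specifies a one-way ANOVA. If overall equality is rejected at 0.1, "then group means will be compared with post-hoc Least Significant Difference (LSD) multiple comparisons", also at 0.1. SAP 8.1 replaces the ANOVA with an MMRM but keeps the gate: "If the treatment effect is significant at the 10% level then the treatment means will be compared using the least significant difference (LSD) method".

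**Power.** Protocol 11.3.3 states: "This study is designed to detect a 30% reduction in annual square root area increase". It uses the SAS one-way ANOVA power procedure with 67 per group and prints 91%, 91% and 83%. The third row reads "0.23 0.28 0.33 67 67 67 83" (per cent). SAP 3.3 claims "approximately 90% power to claim a statistically significant difference in means among treatment groups", assuming a 30% reduction in the APL-2 groups and an SD of 0.2. Neither document gives power for AM vs sham, for AEOM vs sham, or for both.

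**The concern.** A significant F test says that the three means are not all equal. It does not say which regimen beats sham; under the written rule that claim rests on the LSD comparison that follows. The printed power covers the first step only.

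The table shows this itself. Rows 1 and 2 both print 91%, yet in row 2 the AEOM mean equals the sham mean (0.33 and 0.33). A figure that is the same whether or not EOM dosing works cannot be the power of an EOM claim.

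At stake is how a non-significant regimen would be interpreted. Protocol 11.6 bases the Phase III decision and its planning on the one-year analysis, and the choice of regimen may draw on comparisons whose power is stated nowhere.

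**Working it through.** **Inputs**

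- Alpha 0.10, two-sided, for both steps (Protocol 11: "All statistical tests will be two-sided with a type 1 (alpha) error rate of 0.1"; 11.2.3.2).
- Sham growth: "average square root area lesion growth is 0.33mm/year" (Protocol 11.3.1).
- Means AM/AEOM/sham: row 1 0.23/0.23/0.33; row 2 0.23/0.33/0.33; row 3 0.23/0.28/0.33. There are 67 per group, with sham pooled (Protocol 11.3.2, 11.3.3).
- SD 0.20. Protocol 11.3.1 states 0.21, but SAP section 13 confirms that 0.2 was used in the power analysis.

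**Step 1: reproduce the printed figures.** For a one-way ANOVA with 2 and 198 degrees of freedom, the noncentrality is λ = n × Σ(μᵢ − μ̄)² / SD².

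- Rows 1 and 2: Σ(μᵢ − μ̄)² = 0.00667, so λ = 67 × 0.00667 / 0.04 = 11.17. Power is 91.4%.
- Row 3: Σ(μᵢ − μ̄)² = 0.0025 + 0 + 0.0025 = 0.005, so λ = 67 × 0.005 / 0.04 = 8.375. Power is 82.6%.

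These match the printed 91/91/83%. With SD 0.21 the result is 88.8/88.8/79.0%, and with alpha 0.05 (SD 0.20) it is 85.3/85.3/73.2%; neither matches. The printed figures are therefore F-test power at SD 0.20 and alpha 0.10.

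**Step 2: the LSD step.** The standard error of a difference is 0.20 × √(2/67) = 0.0346 mm. With a critical t of 1.653 (198 df), the least significant difference is 1.653 × 0.0346 = 0.057 mm. The design effect of 0.10 mm is well above this. The row 3 EOM effect of 0.05 mm is below it, so an EOM estimate equal to its true value would not be significant.

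**Step 3: the two-step rule.** Group means and the pooled variance were simulated (1,000,000 replicates per row). A claim for an arm required F to reject at 0.10 and then its LSD t test against sham to reject at two-sided 0.10 in favour of APL-2. Results at SD 0.20:

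| Row | Printed | F test | AM vs sham | AEOM vs sham | Both | At least one |
|---|---|---|---|---|---|---|
| 1 | 91% | 91.4% | 86.4% | 86.4% | 81.4% | 91.4% |
| 2 | 91% | 91.4% | 86.4% | 5.0%* | 5.0%* | 86.4% |
| 3 | 83% | 82.6% | 81.7% | 40.7% | 40.3% | 82.1% |

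*EOM has no true effect in row 2, so these are false-positive rates.

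Two cross-checks:

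- In row 1 an F rejection almost always comes with at least one arm beating sham, so both = 86.4 + 86.4 − 91.4 = 81.4%.
- In row 2 the gap between the F test and at least one arm is 91.4 − 86.4 = 5.0 points: trials in which F rejects but neither APL-2 arm is shown superior to sham.

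**Step 4: the protocol's stated SD of 0.21.** Row 1: each arm 83.0%, both 77.2%. Row 2: AM 83.0%. Row 3: AM 77.8%, AEOM 37.8%, both 37.2%.

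**The case against.** The case on the other side is substantial.

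- **Nothing printed is miscalculated or mislabelled.** The protocol names the one-way ANOVA procedure and heads the column as power to detect a difference; the SAP speaks of a difference among groups. The formal null hypothesis is the overall one, and the pairwise tests are called post hoc. This stands. A reader might infer that the power table is wrong; the documents do not support that.
- **The aim can be read as either regimen.** Protocol 5.3 joins the regimens with *and*, which most naturally means each of them, but 11.2.3 says *either ... or*. On the second reading power is 91.4/86.4/82.1%, so rows 1 and 3 stand and only row 2 falls short, by about 5 points. A reader might infer that the trial is badly underpowered for its aim; that does not follow while the aim is open to both readings.
- **The 40% is not power at the design effect.** In row 3 EOM growth falls from 0.33 to 0.28, a reduction of 0.05/0.33 = 15%, half the target. Low power there is expected. It still matters, because row 3 is the plan's own scenario and its 83% holds for the F test but not for an EOM claim.
- **Pairwise results are reported anyway.** SAP 8.1 presents all three treatment comparisons with estimate, standard error and 95% CI; only the LSD p-value depends on the gate. No passage says that a non-significant EOM result will be taken as no effect. This stands, and no further reporting commitment is needed.
- **The SAP uses an MMRM adjusted for baseline.** Its power may differ, but the documents give no correlations with which to compute it. The figures here belong to the protocol's ANOVA and must be labelled so.

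**Conclusion.** The point holds as a gap in what is stated, not as an error of calculation. At the 30% design effect, the rule that supports a superiority claim has about 86% power for each regimen and about 81% for both, against a printed 91%. If only AM works, AM has about 86%, not 91%. In row 3 the figures are about 82% for AM, 41% for AEOM and 40% for both, beside a printed 83%.

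These results assume 67 evaluable subjects per group, SD 0.20, normal outcomes with equal variances, and the protocol's ANOVA with LSD. At SD 0.21 the power for both falls to about 77% (row 1) and 37% (row 3). How large the shortfall is depends on whether the aim is both regimens or at least one, which the protocol leaves unsettled.

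**What to change.** 1. **Protocol 11.3.3.** Relabel the last column as power of the overall F test, state the SD used, and add columns for the F-then-LSD rule: AM vs sham, AEOM vs sham, both, and at least one. At SD 0.20 these are 86/86/81/91% (row 1), 86/5/5/86% (row 2, with the 5% marked as a false-positive rate) and 82/41/40/82% (row 3).
2. **Protocol Synopsis, 5.3 and 11.2.3.** Use one wording of the aim: superiority of both regimens, or of at least one.
3. **SAP 3.3.** Say that the approximately 90% is for the overall test. Give the per-comparison figures and mark them as based on the protocol's one-way ANOVA, not on the SAP's MMRM.

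The cost is wording and one recomputed table. Sample size, design and analysis do not change; the stated figures become less favourable.

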11.3.4 Drop out/Loss to follow up

We assume a 15-20% loss to follow up. Accordingly, inflation of the sample size in (d) Total N = 201÷83.5% suggests recruitment of 240 subjects should be sufficient.

11.4 Safety Assessment

Adverse events will be collected from the time of the first study drug administration until a subject completes the study or discontinues prematurely. A treatment-emergent adverse event is defined as any new adverse event reported or any worsening of an existing condition on or after the first dose of study drug. Treatment-emergent adverse events will be summarized by treatment group.

Adverse events will be summarized by MedDRA coding terms, and separate tabulations also will be produced for related adverse events (those considered by the PI as definitively drug related),

serious adverse events and discontinuations due to adverse events. Vital signs data and findings from physical and ophthalmologic examinations will be tabulated for changes over time on study. Laboratory parameters will be summarized for changes across study by using descriptive statistics.

11.5 Handling of Missing Data

All efforts will be made to minimize missing data. For the primary efficacy endpoint (12 month mITT), we will impute using the last observation prior to month 12. However, if there is an imbalance in loss to follow up by treatment group, we will employ a regression method of imputation. The reason for this is a scenario in which fewer subjects in the actively treated arms complete follow up. Use of their, for example, 2 month visit lesion areas in the efficacy analysis would artificially decrease the mean growth estimates in the actively treated groups.

11.6 Interim analyses

We do not plan a formal interim analysis and so have not adjusted alpha for one. The decision to pursue a phase III trial and the planning for it will be based on the one year follow up analysis. That is, while a six-month analysis may be performed, even a statistically significant effect would not result in discontinuation of the Phase II trial and implementation of a Phase III study.

11.7 Exploratory Efficacy Endpoints

Other variables used for efficacy analyses will include lesion growth measurements by SD-OCT and change in visual acuity (letters read).

11.8 Randomization

The methods for generating the randomization schedule and for assigning study subjects to treatment arms will be described in a separate Randomization Plan and Specifications Document and included in the MOP.

12. ETHICS

12.1 Ethical Conduct of the Study

This research will be carried out in accordance with the protocol, US Code of Federal Regulations (21 CFR Parts 50, 56, and 312) GCP, the ethical principles set forth in the Declaration of Helsinki, and the ICH harmonized tripartite guideline regarding GCP (E6 Consolidated Guidance, April 1996).

12.2 Institutional Review Board/Ethic Committee

The study protocol, any amendments to the protocol, ICF, the Investigator's Brochure, and other study specific information will be reviewed and approved by the IRB/IEC. The study will not be initiated until the IRB/IEC has approved the protocol or a modification thereof. All records pertaining to IRB/IEC submission and approval should be kept in the site's regulatory files and Sponsor's Trial Master File.

The IRB/IEC must be constituted and operate in accordance with the principles and requirements described in the US Code of Federal Regulations (21 CFR Part 56) and/or ICH Guidelines, or other local regulations as deemed appropriate.

12.3 Subject Information and Consent

The Investigator is responsible for obtaining an informed consent. A written informed consent, in compliance with the US Code of Federal Regulations (21 CFR Part 50) and/or ICH Guidelines, must be obtained from each subject prior to screening and enrollment or performing any study related procedures.

The purpose of the study, the procedures to be carried out and the potential hazards will be described to the subjects in non-technical terms. The subject will be given sufficient time to consider the study's implications before deciding to participate in the study. The subject and/or legal guardian will be required to sign and date an ICF and will be assured that they may withdraw from the study at any time without jeopardizing their medical care. The Investigator shall retain the original, signed ICF for study participation in the subject's medical record and shall provide the subject and/or legal guardian with a copy of the signed ICF.

If there are any changes/amendments to the approved protocol, which may directly affect the subject's decision to continue participation in the study, the ICF shall be amended to incorporate the changes to the protocol and the subject must re-sign the IRB/IEC approved amended ICF.

12.4 Confidentiality

Confidentiality of subjects information must be maintained in accordance with the Health Insurance Portability and Accountability Act (HIPAA) Privacy Rule-Final Modification (45 CFR Parts 160 and 164), ICH Guidelines, and/or any other local guidelines and regulations.

13. ADMINISTRATIVE CONSIDERATIONS

13.1 Direct Access to Source Data/Documents

The Investigator must maintain, at all times, the primary records (i.e. source documents) of each subject's data for data verification. Examples of source documents are medical records, laboratory reports, study drug records, and printed CRF pages that are used as the source.

The Investigator will permit trial-related monitoring, audits, and inspections by the Sponsor and/or its' designee, IRB/IEC, and the regulatory agencies at any time during the study. The Investigator will ensure that the auditor is allowed direct access to the source data, medical records, eCRFs, and the Site's regulatory file for the study and any other pertinent information.

13.2 Quality Control and Quality Assurance

This study is to be performed in full compliance with the protocol, GCP, and applicable regulatory requirements. The Investigator, Sponsor and/or its' designee are responsible for ensuring that the study staff receive appropriate training on the protocol, study procedures and any other relevant information.

Quality assurance and quality control systems are implemented and maintained using written Investigative site, Sponsor and/or designee Standard Operating Procedures (SOPs) to ensure that the study is conducted and data are generated, documented (recorded), and reported in compliance with the protocol, GCP, and the applicable regulatory requirement(s) and local laws, rules, regulations.

Quality control (QC) checks will be applied at each stage of data handling (e.g. edit checks) to ensure that all data are reliable and have been processed correctly.

13.3 Monitoring

On-site monitoring will be performed by the Sponsor's designee for the duration of the study. The monitor will ensure that the study is conducted, recorded and reported in accordance with the protocol, SOPs, GCP, and the applicable regulatory requirements. The monitor will verify the accuracy and completeness of the eCRF entries, source documents, and other study-related records against each other. The Investigator will provide direct access to source data/documents for study-related monitoring. It is important that the Investigator and the Investigator Site staff are available at these visits. The monitor will record the date of each visit together with a summary of the status and progress of the study. Proposed actions will be documented in writing to the Investigator.

13.4 Data Handling and Record Keeping

The Investigator must maintain all documentation related to this study. All essential documents (as defined in the ICH Guideline E6) and the data generated in connection with this study, together with the original copy of the final report, will be retained for at least 2 years after the last approval of a marketing application in an ICH region and until there are no pending or contemplated marketing applications in an ICH region or at least 2 years have elapsed since the formal discontinuation of clinical development of the investigational product. All essential documents generated in connection with this study in Australia and New Zealand must be retained for at least 15 years after study completion. These documents should be retained for a longer period if required by the applicable regulatory requirements or by an agreement with the Sponsor.

It is the responsibility of the Sponsor to inform the Investigator/Institution as to when these documents no longer need to be retained.

13.5 Protocol Amendments

Any amendments to the study protocol deemed necessary as the study progresses will be discussed between Sponsor and the Investigator. The Investigator will not implement any changes to the protocol without an agreement by the Sponsor and prior review and documented approval/favorable opinion from the IRB/IEC of an amendment, except where necessary to eliminate immediate hazards to study subject or when the changes involve only logistical or administrative aspects of the study (e.g. change in staff, telephone numbers).

Changes resulting in amendments will be made jointly between the Sponsor and the Investigator and must be confirmed in writing. Amendment(s) will be approved and signed off in the same way as the protocol.

13.6 Report Format

According to the ICH Harmonized Tripartite Guideline (Organization of the Common Technical Document for the Registration of Pharmaceuticals for Human Use M4 and the ICH M2 Expert Working Group), the final report will be written according to the ICH E3 Guideline (Structure and Content of Clinical Study Reports).

13.7 Finance and Insurance

Finance and insurance will be addressed in a Clinical Trial Agreement between the Sponsor and the Investigator/Institution.

13.8 Publication Policy

The data generated for this study are considered confidential information and are the property of the Sponsor. All study information provided to the Investigator and Site personnel by the Sponsor shall not be published or disclosed to a third party without the prior written consent of the Sponsor.

After the completion of the study, the data may be reported at a scientific meeting and/or submitted for publication in a scientific journal with the prior written consent of the Sponsor. The Sponsor must be given at a minimum 30 days to review the materials to be presented at a scientific meeting and/or for publication in a scientific journal.

